8.4.3 Record Retention

All study records must be retained for at least 25 years after the end of the clinical trial or in accordance with national law. Subject files and other source data must be kept for the maximum period of time permitted by the hospital, institution or private practice, but not less than 25 years. Ultragenyx must be notified and will assist with retention should the Investigator/institution be unable to continue maintenance of subject files for the full 25 years. All study records must be stored in a secure and safe facility.

8.5 Reporting and Follow-up of Adverse Events

8.5.1 Definition of Adverse Events

An AE is defined as any untoward medical occurrence associated with the use of a drug in humans, whether or not considered drug related. An AE can therefore be any unfavorable and unintended sign (including an abnormal laboratory finding, for example), symptom, or disease temporally associated with the use of a medicinal (investigational) product, whether or not related to the medicinal (investigational) products.

A suspected adverse reaction is any AE for which there is a reasonable possibility that the drug caused the AE. For the purposes of expedited safety reporting, “reasonable possibility” means there is evidence to suggest a causal relationship between the drug and the AE. Suspected adverse reaction implies a lesser degree of certainty about causality than adverse reaction, which means any AE caused by a drug.

Life-threatening AE or life-threatening suspected adverse reaction is an AE or suspected adverse reaction that, in the view of either the investigator or sponsor, places the patient or subject at immediate risk of death. It does not include an AE or suspected adverse reaction that, had it occurred in a more severe form, might have caused death.

An SAE or serious suspected adverse reaction is an AE or suspected adverse reaction that at any dose, in the view of either the investigator or sponsor, results in any of the following outcomes:

- Death
- A life-threatening AE
- Inpatient hospitalization or prolongation of existing hospitalization
- Persistent or significant incapacity or substantial disruption of the ability to conduct normal life functions
- A congenital anomaly/birth defect

Important medical events that may not result in death, be immediately life-threatening, or require hospitalization may be considered serious when, based upon appropriate medical judgment, they may jeopardize the patient or subject and may require medical or surgical intervention to prevent one of the outcomes listed in the definition.

Note that hospitalizations planned prior to study enrollment (e.g. for elective surgeries) are not considered SAEs. Hospitalizations that occur for pre-existing conditions that are scheduled after study enrollment are considered SAEs.

8.5.2 Severity of Adverse Events

Wherever possible, the severity of all AEs will be graded using the NCI CTCAE version 4.0. The majority of AEs can be graded using this system.

If an AE cannot be graded using the CTCAE criteria, it should be graded as mild, moderate, severe, life-threatening, or death using the following definitions.

- ***Mild (Grade 1):*** Awareness of signs or symptoms, but easily tolerated and are of a minor irritant type, causing no loss of time from normal activities. Symptoms do not require therapy or a medical evaluation; signs and symptoms are transient.
- ***Moderate (Grade 2):*** Events introduce a low level of inconvenience or concern to the participant and may interfere with daily activities, but are usually improved by simple therapeutic measures; moderate experiences may cause some interference with functioning.
- ***Severe (Grade 3):*** Events interrupt the participant's normal daily activities and generally require systemic drug therapy or other treatment; they are usually incapacitating.
- ***Life-threatening (Grade 4):*** Events that place the participant at immediate risk of death or disabling.
- ***Death (Grade 5):*** Events that result in death.

To ensure that there is no confusion or misunderstanding of the difference between the terms "serious" and "severe," which are not synonymous, the following note of clarification is provided. The term "severe" is often used to describe the intensity (severity) of a specific

event (as in mild, moderate, or severe myocardial infarction); the event itself, however, may be of relatively minor medical significance (such as severe headache). This is not the same as "serious" which is based on subject/event outcome or action criteria usually associated with events that pose a threat to a subject's life or functioning. Seriousness (not severity) serves as a guide for defining regulatory reporting obligations.

8.5.3 Relationship of Adverse Events to Study Drug

The investigator will assess the potential relationship of the AE to study drug using the following descriptions.

Categories of attributions for “Not Related” events:

- ***Definitely Not Related:*** This category applies to an AE that *is clearly not related* to the investigational agent/procedure, beyond a reasonable doubt. That is, another cause of the event is most plausible; and/or a clinically plausible temporal sequence is inconsistent with the onset of the event and the exposure to study drug and/or a causal relationship is considered biologically implausible.
- ***Probably Not Related:*** This category applied to an AE that *is doubtfully related* to the investigational agent/procedure. That is, an alternative explanation is more likely, e.g., concomitant drug(s), concomitant disease(s), known consequences of the disease under investigation or the relationship in time suggest that a causal relationship is unlikely.

Categories of attributions for “Related” events:

- ***Possibly Related:*** This category applies to an AE that *may be related* to the investigational agent/procedure. That is the AE follows a reasonable temporal sequence from administration of the study drug and that follows a known or expected response pattern to the suspected study drug, but that could readily have been produced by a number of other factors.
- ***Probably Related:*** This category applies to an AE that *is likely related* to the investigational agent/procedure. That is, the AE has a temporal relationship to the administration of the investigational agent(s) or research intervention, follows a known or suspected pattern of response, and is strongly associated with study drug exposure. An alternative explanation is less likely (e.g., concomitant drugs(s), concomitant medication(s)).
- ***Definitely Related:*** This category applies to an AE that *is clearly related* to the investigational agent/procedure. That is, the AE is listed as a possible adverse reaction and cannot be reasonably explained by an alternative explanation, e.g., concomitant drug(s), concomitant disease(s), known consequences of the disease under investigation or the relationship in time is very suggestive (e.g., it is confirmed by dechallenge and rechallenge).

For regulatory reporting purposes, AEs deemed as Definitely, Probably, or Possibly Related will be considered Related, and those deemed Definitely Not or Probably Not Related will be considered Unrelated.

8.5.4 Adverse Event Reporting to Ultragenyx

All AEs (i.e., any new or worsening in severity or frequency of a pre-existing condition) with onset after the subject signs informed consent must be promptly documented on the AE eCRF via the EDC system. The Principal Investigator is responsible for evaluating all AEs, obtaining supporting documents, and ensuring documentation of the event is adequate. Details of the AE must include severity, relationship to study drug, duration of AE (with start and stop dates, as applicable), and outcome.

All AEs will be collected from the time the subject signs informed consent through their EoT Visit or final Safety Follow-up TC as outlined in Section 7.1. In addition, the investigator may report any AE that occurs after this time period that is believed to have a reasonable possibility of being associated with study drug. For AEs that are ongoing beyond the follow-up telephone call (Week 152), the investigator should comment in the source document whether the event has recovered, recovered with sequelae, or stabilized.

8.5.5 Serious Adverse Events, Serious Adverse Drug Reactions, and Requirements for Immediate Reporting

Ultragenyx or its designee must be notified of the occurrence of any SAE that occurs during the reporting period within 24 hours of the investigator's, designee's, or site personnel's knowledge of the event. SAEs will be reported by completing and submitting an SAE report from the investigator to Ultragenyx or its designee.

Follow-up SAE information must be submitted in a timely manner as additional information becomes available. All SAEs, regardless of relationship to study drug, must be followed to resolution or stabilization if improvement is not expected.

All deaths, regardless of causality, that occur from signing of the informed consent through EoT Visit or final Safety Follow-up TC (Section 7.1) must be reported as SAEs as described previously.

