19 After proper training, subjects or their caregiver will administer study drug under the supervision of a healthcare provider. If the subject or caregiver demonstrates competency in administration of SC injections at that time, they will be instructed to perform future study drug administrations at home without supervision for HH visits occurring after week 96 or later (with the exception of site visits, during which subject/caregiver administration is preferable to demonstrate continued competency in technique, but not required). Drug administration by a HH nurse may continue at the discretion of the investigator, subject and/or caregiver. If the healthcare provider determines that the subject/caregiver requires additional training on SC injection technique, study drug will again be administered under the supervision of a healthcare provider at the next study visit. Once a subject or their caregiver has received appropriate SC injection technique training and begins administering study drug at home without supervision, they will be contacted via telephone by the study site every 28 days (+ 5 days), with the exception of site visits, to confirm administration of study drug and to record concomitant medications and AEs. Telephone visits may also be conducted at the clinical site depending on proximity of the subject to the site.

20 For subjects that are self-administering or having a caregiver administer study drug, a healthcare provider will return for HH visits occurring every 12 weeks after week 96 or visit 32 to assess vital signs, pregnancy, and record concomitant medications and AEs.

21 If a subject will be continuing KRN23 treatment under commercial use or another mechanism, the first dose of that treatment should not be administered until after completion of all of the EoT Visit assessments. Those subjects who terminate the study early will be asked to come back to the clinic for a final assessment. If the subject terminates the study early before Week 72, then the Week 72 assessments will be conducted. If the subject terminates the study early between Weeks 72 and EoT Visit (up until 30 September 2018, occurring within 4 weeks of last dose administration), then the EoT assessments will be conducted. Every reasonable effort should be made to have subjects return to the clinic for the final assessment.

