22 To be completed for all subjects who complete the EoT Visit and are not immediately continuing KRN23 treatment under commercial use or another mechanism. The site personnel will initiate a Safety Follow-up telephone call (TC) 4 weeks (+ 5 days) after the EoT Visit to collect information on whether KRN23 treatment has been started through another mechanism and, if not, any ongoing or new AEs, serious adverse events (SAEs), or concomitant medications. Appropriate follow-up of AEs/SAEs should continue until all safety concerns, in the Investigator's opinion, are resolved. If the subject is not continuing KRN23 therapy under commercial use or another mechanism at that time, then site personnel will initiate a subsequent

Protocol Number: UX023-CL203
Amendment 2
29 September 2017

Safety Follow-up TC at 8 weeks (+ 5 days) after the EoT Visit to collect information on whether KRN23 treatment has been started through another mechanism and, if not, any ongoing or new AEs, SAEs, or concomitant medications.

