If a subject discontinues from the study prematurely, every reasonable effort should be made to perform the EoT Visit procedures within four weeks of discontinuation. If the subjects will be continuing KRN23 treatment under commercial use or another mechanism, all EoT assessments should be performed before beginning that treatment. For subjects not immediately continuing KRN23 treatment under commercial use or another mechanism, a Safety Follow-up TC will occur 4 weeks (+ 5 days) after the EoT visit to collect information on whether KRN23 treatment has been started through another mechanism and, if not, any ongoing or new AEs, SAEs, or concomitant medications. If the subject is not continuing KRN23 therapy under commercial use or another mechanism at that time, then site personnel will initiate a subsequent Safety Follow-up TC 8 weeks (+ 5 days) after the ET Visit to collect information on whether KRN23 treatment has been started through another mechanism and, if not, any ongoing or new AEs, SAEs, or concomitant medications.

Subjects who withdraw or are removed from the study after receiving study drug may be replaced on a case-by-case basis, at the discretion of Ultragenyx.

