7.5.3.11 Pregnancy Testing

Female subjects of child-bearing potential must be non-pregnant and non-nursing and will have urine pregnancy tests pre-dose at all dosing visits and at EoT, as indicated in [Table 2.1](#) and [Table 2.2](#). A serum pregnancy test will be performed in the event of a positive or equivocal urine pregnancy test result. In the event of a positive urine pregnancy test at an HH visit, KRN23 will not be administered and a serum sample will be drawn for confirmation of pregnancy. Female subjects with a positive serum pregnancy test at Screening will not be enrolled in the study. Female subjects with a positive serum pregnancy test at Baseline or any subsequent visit will be discontinued from the study.

Experience with KRN23 in pregnant women is limited. The study drug may involve risks to a pregnant female or unborn baby that are currently unknown. Female participants of child-bearing potential who have not undergone a total hysterectomy or bilateral salpingo-oophorectomy and are sexually active must consent to use a highly effective method of contraception as listed below from the period following the signing of the informed consent through 12 weeks (approximately 5 times the elimination half-life) after stopping the study drug. Sexually active male participants with female partners of childbearing potential must consent to use a condom with spermicide or a highly effective method of contraception

listed below from the period following the signing of informed consent through 12 weeks after stopping the study drug. Examples of highly effective methods include:

- Combined (estrogen and progestogen containing) hormonal contraception associated with inhibition of ovulation (e.g. oral, intravaginal, transdermal)
- Progestogen-only hormonal contraception associated with inhibition of ovulation (e.g. oral, injectable, implantable)
- Intrauterine device (IUD) or intrauterine hormone-releasing system (IUS)
- Bilateral tubal occlusion
- Male sterilization, also called vasectomy
- Sexual abstinence (i.e., refraining from heterosexual intercourse during the entire period of risk associated with the study treatments, when this is in line with the preferred and usual lifestyle of the subject)

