7.5.3.12 Pregnancy in Subject or Partner

Pregnancies in subjects or partners must be reported within 24 hours of knowledge of the event to Ultragenyx or its designee. The reporting period for pregnancies is the period from the signing of the ICF through the EoT Visit or final Safety Follow-up TC, as defined in Section 7.1. Reported pregnancy of a subject or a subject's partner, while participating in the study, will be monitored for the full duration and/or followed until the outcome of the pregnancy is known. In the event of a pregnancy in the partner of a subject, the investigator should make every effort to obtain the female partner's consent for release of protected health information. Refer to the Study Reference Manual for details on the reporting procedures to follow in the event of pregnancy.

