8.5.7 Communication Plan

Ultragenyx or its designee will submit SUSAR reports to appropriate regulatory authorities and investigators as per local laws and regulations. Fatal and life-threatening SUSARs will be submitted no later than 7 calendar days of first knowledge of the event and follow-up information will be submitted within an additional eight (8) days. All other SUSARs will be submitted within 15 calendar days of first knowledge of the event.

Principal Investigators are required to report any urgent safety matters to Ultragenyx or its designee within 24 hours. Ultragenyx or its designee will inform the regulatory authorities and investigators of any events (e.g., change to the safety profile of KRN23, major safety findings) that may occur during the clinical trial that do not fall within the definition of a SUSAR but may affect the safety of subjects participating in the clinical trials, as required in accordance with applicable laws and regulations. The reporting period for urgent safety issues is the period from signing the informed consent through 12 weeks following the last dose of study drug.

The investigator is responsible for notifying the IRBs of SAEs and any urgent safety matters, in accordance with IRB requirements and local laws and regulations. A copy of this notification must be provided to Ultragenyx or its designee.

Non-SUSARs will be maintained in the Ultragenyx safety database and provided in annual and/or periodic reports as per local laws and regulations. Ultragenyx or its designee will prepare and submit annual safety reports and/or other aggregate periodic summary reports to regulatory authorities, as required

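### For some early withdrawals, collection of adverse events and pregnancies can close up to 4 weeks before the protocol's own 12-week post-dose period ends

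*Protocol*

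**What the plan says.** The protocol runs two clocks after treatment stops.

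- **Clock tied to the visit.** Section 8.5.4: "All AEs will be collected from the time the subject signs informed consent through their EoT Visit or final Safety Follow-up TC". Sections 7.5.3.1 (adverse events) and 8.5.5 (deaths) use the same end point. For pregnancies, Section 7.5.3.12 says "The reporting period for pregnancies is the period from the signing of the ICF through the EoT Visit or final Safety Follow-up TC". For early discontinuation, Section 7.3.3 describes the last contact as a "subsequent Safety Follow-up TC 8 weeks (+ 5 days) after the ET Visit".
- **Clock tied to the last dose.** Section 7.5.3.11 requires contraception "through 12 weeks (approximately 5 times the elimination half-life) after stopping the study drug". Section 8.5.7 keeps urgent safety issues reportable "through 12 weeks following the last dose of study drug".

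The EoT visit of an early withdrawal has an upper time limit and no lower one. Footnote 21 to Tables 2.1 and 2.2, covering terminations after Week 72, has it "occurring within 4 weeks of last dose administration". Section 7.3.3 asks for it within four weeks of discontinuation.

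Footnote 22 describes the calls as "To be completed for all subjects who complete the EoT Visit and are not immediately continuing KRN23 treatment" by another route. Section 7.5 also covers early withdrawal, but it times the second call from the subject's final study site visit. Section 8.5.4 still labels the follow-up call Week 152, a week that Table 2.2 now lists among the 4-weekly contacts with drug administration.

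**The concern.** Long-term safety is the first primary objective. The protocol treats 12 weeks after the last dose, about five half-lives, as the period in which exposure still matters, yet scheduled collection is not tied to the last dose. The two clocks coincide for scheduled completers, which suggests that the difference for early withdrawals was not intended.

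What is at stake is the systematic capture of new events, deaths and pregnancies in roughly Weeks 9 to 12 after the last dose, in some subjects who leave early. A pregnancy arising then would fall within the contraception period but could fall outside the reporting period. SAP Section 8.6.1 gives treatment-emergent events a start and no end, so under that definition the collection window decides which late events can be counted.

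**Working it through.** **Inputs**

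- Half-life 322 to 448 hours (Protocol 7.2): 322/24 = 13.42 days and 448/24 = 18.67 days.
- Post-dose period 12 weeks = 84 days (7.5.3.11, 8.5.7).
- Final call at EoT/ET + 8 weeks = 56 days, with +5 days allowed (7.1, 7.3.3, 7.5.3.1, footnote 22).
- At most 46 doses and 184 weeks of treatment (Synopsis), and at most 192 weeks on study (7.1).
- Last dose at the visit before EoT (7.1, 7.4.1).

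**1. The protocol's own figure.** 5 × 13.42 = 67.1 days (9.6 weeks), and 5 × 18.67 = 93.3 days (13.3 weeks). Twelve weeks lies in this range, so the description as about five half-lives is reproduced.

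**2. Scheduled completer on the longest schedule.** Doses at Weeks 0, 4, …, 180 number 180/4 + 1 = 46. EoT is at Week 184 and the final call at Week 192. 192 − 180 = 12 weeks after the last dose, so the shortfall is 0.

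**3. Early withdrawal.** Let g be the weeks from last dose to EoT/ET. The final call is at g + 8 weeks. The shortfall is max(0, 84 − 7g − 56) days, or max(0, 84 − 7g − 61) days if all 5 extra days are used.

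| g (weeks) | Final call (weeks after last dose) | Shortfall (days) | Shortfall with +5 days |
|---|---|---|---|
| 0 | 8 | 28 | 23 |
| 1 | 9 | 21 | 16 |
| 2 | 10 | 14 | 9 |
| 3 | 11 | 7 | 2 |
| 4 | 12 | 0 | 0 |

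The worst case is 28/84 = 33% of the period. For g above 4 there is no shortfall. For example, g = 8 gives a final call at 16 weeks.

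**4. In half-lives.** Assuming first-order elimination, the fraction remaining is 2^(−days/half-life).

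- At 56 days: 56/13.42 = 4.17 and 56/18.67 = 3.00 half-lives, leaving 5.5% to 12.5%.
- At 84 days: 84/13.42 = 6.26 and 84/18.67 = 4.50 half-lives, leaving 1.3% to 4.4%.

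**5. No EoT visit.** Under footnote 22 such a subject is outside the group to be called. Under Section 7.5 the second call has a usable date, the final site visit, but the first call is still timed from EoT. The two passages give different answers.

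**The case against.** **Four weeks is an extreme.** It needs the EoT visit at about the day of the last dose. Section 7.3.3 counts from discontinuation, so a subject who withdraws at the next 4-weekly contact may have EoT 4 to 8 weeks after the last dose and the final call at 12 to 16 weeks. This stands. The gap runs from 0 to 4 weeks and is not a fixed loss.

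**The protocol has other nets.** Section 8.5.4 lets investigators report later events thought related. Footnote 22 continues follow-up of adverse events until safety concerns resolve. Section 8.5.7 keeps urgent issues open to 12 weeks. This stands in part. The event that caused withdrawal should be followed, so new-onset events and pregnancies are what is exposed. For those, reporting is discretionary or confined to urgent matters, and no scheduled contact prompts it.

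**Few subjects are involved.** Enrolment is 20, so each is 5% of the safety set, and the documents give no number of withdrawals. Treatment lasts 156 to 184 weeks and ends by 30 September 2018 (7.4.5). At the amendment's date of 29 September 2017, about 52 weeks earlier, subjects still treated were at about Weeks 104 to 132. Only withdrawals from then on are affected. This stands.

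**Late events might not be tabulated anyway.** Protocol 7.6.2.8.1 describes treatment-emergent events as having onset during treatment, whereas SAP 8.6.1 sets no end. The effect on the summary tables is therefore uncertain.

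**A 12-week limit would not catch every pregnancy.** A conception in Weeks 9 to 12 may not be recognised by Week 12. That limits the benefit for pregnancies but does not justify an earlier close.

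A reader might infer that a subject without an EoT visit loses all post-treatment follow-up. Section 7.5 does not support that, because it supplies a date for the second call; the fault is conflicting wording. A reader might also infer that safety signals will be missed mainly in those who leave because of an event. The documents give no data to show it.

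**Conclusion.** The point holds in bounded form. Scheduled collection of new adverse events, deaths and pregnancies can end 0 to 4 weeks before the protocol's own 12-week period in subjects who withdraw early and are followed off drug. The maximum is 28 days, or 23 if the full call window is used. Scheduled completers have no gap, nor does anyone whose EoT visit is 4 or more weeks after the last dose.

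This rests on two assumptions. The first is that the visit can follow the last dose closely, which the text permits but does not make likely. The second is that completers' last dose is at the visit before EoT. Section 7.4.6 instead has injections continuing through 30 September 2018, the date by which EoT must occur, and must be reconciled with Sections 7.1 and 7.4.1. Subjects who move to non-study KRN23 are a separate case: study collection can stop sooner, but they are exposed again.

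The conflict over subjects with no EoT visit and the outdated Week 152 label are wording faults in the current text. The whole matter is worth correcting because the correction is cheap, not because a large loss of data has been shown.

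**What to change.** In Sections 7.1, 7.3.3, 7.5, 7.5.3.1, 7.5.3.12, 8.5.4, 8.5.5 and footnote 22, end collection of adverse events, serious events, deaths and pregnancies at the **later** of 8 weeks after the EoT/ET visit and 12 weeks after the last study dose, or at the start of non-study KRN23 after EoT if that comes first. Time the final call to that date.

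The later of the two clocks is needed because Sections 7.4.6 and 7.4.8 allow doses to be delayed or skipped. If the last dose was 8 weeks before EoT, the current text collects to 8 + 8 = 16 weeks, and a plain 12-week limit would cut that by 4 weeks.

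Apply the rule to every treated subject not continuing KRN23, whether or not the EoT visit took place, and reconcile footnote 22 with Section 7.5. Where there was no EoT visit, the final site visit already named in Section 7.5 can stand in for it. In Section 8.5.4, replace Week 152 with a reference to the final safety follow-up call.

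The cost is amendment wording and a final call up to 4 weeks later for some early withdrawals. There are no new visits or samples, and no subject's collection is shortened.
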